## 5.2 Trial Treatments

### 5.2.1 Dose Selection/Modification

#### 5.2.1.1 Dose Selection

Please refer to [Section 4.2.2](#).

If Stage 1 proceeds without the need for any dose modification as described in [Section 5.2.1.2.1](#), Imprime PGG will be administered to all subjects at a dose of 4 mg/kg IV over a 2-hour infusion time period on Day 1, Day 8, and Day 15 of each 3-week cycle. Refer to [Appendix 14.1](#) for further details.

If enrollment into an additional cohort in Stage 1 is necessitated based on the dose modification requirements as described in [Section 5.2.1.2.1](#), Imprime PGG will be administered to all subjects in the specified indication at a dose of 2 mg/kg IV over a 2-hour infusion time period on Day 1, Day 8, and Day 15 of each 3-week cycle. Refer to [Appendix 14.1](#) for further details.

Imprime PGG will always be administered first, followed 15-30 minutes later only on Day 1 of each cycle by pembrolizumab administration.

The pembrolizumab fixed dose of 200 mg will be administered IV over 30 minutes on Day 1 of each 3-week treatment.

#### 5.2.1.2 Dose Modification

##### 5.2.1.2.1 Imprime PGG

Each cycle will be 3 weeks in duration. The dose of Imprime PGG may be delayed or reduced as described below, due to the occurrence of infusion reactions or other adverse events.

Per CTCAE guidelines, mild-to-moderate reactions (Grades 1 and 2) are characterized by flushing, rash, fever, rigors, chills, dyspnea, nausea, back pain, and mild hypotension. Severe reactions (Grades 3 and 4) are associated with bronchospasm and hypotension requiring treatment, cardiac dysfunction, anaphylaxis, abdominal cramping, and other symptoms. The preferred order for actions the Investigator may take to ameliorate infusion reactions are listed below:

###### 1. Premedication(s)

Subjects may receive pre-treatment with standard anti-histamine medications before commencing dosing of study medications on each treatment day and, as needed, post-dose.

Premedication:

- Cycle 1/Day 1: Pretreat with an H1 antagonist (eg, 50 mg of diphenhydramine IV)

- Subsequent cycles: Premedication is allowed for each Imprime PGG infusion, but if tolerated by the subject and if medically appropriate, reduced premedication doses from those administered at Cycle 1/Day 1 should be used

## **2. Infusion Time Extension**

The infusion time should be lengthened from 2 hours to 4 hours and the infusion flow rate should be adjusted accordingly to 50% of the previous rate.

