## **3. Dose Reduction**

If a subject experiences an infusion reaction despite having been administered premedication and despite the infusion time being lengthened, the PI may re-challenge the subject at the next visit by dose reducing the Imprime PGG to 2 mg/kg.

All attempts should be made to ameliorate Grade 3/4 infusion reactions by the Investigator following the 3 recommendations provided above sequentially.

In Stage 1, any Grade 3/4 infusion reactions mitigated by these actions and either resolving or decreasing to Grade 1/2, if this mitigation occurs within Cycle 1 and the Grade 3/4 infusion reaction does not recur in Cycle 2, will not be counted towards the total of > 4 or 33% of Grade 3/4 adverse events which require halting the study in Stage 1 for each individual indication. Only Cycle 1 Grade 3/4 infusion reactions (or those which recur in Cycle 2) will be counted towards the total which would halt advancement to Stage 2.

- In the event there are a total of > 4 or 33% of Grade 3/4 adverse events in Stage 1 which were unable to be ameliorated by the sequential recommendations above, the dose of Imprime PGG will be reduced to 2 mg/kg.
- Stage 1 will be repeated with an additional cohort of n=12 subjects at the reduced dose of 2 mg/kg. Toxicity at the dose of 2 mg/kg will be assessed in this additional Stage 1 cohort in the same manner as was done for the initial dose of 4 mg/kg, with the identical sequential recommendations for any observed infusion reactions.
- Advancement to Stage 2 will be halted if there are > 4 or 33% of Grade 3/4 adverse reactions. Otherwise, subjects will proceed to Stage 2 with all subjects at the new, reduced dose of 2 mg/kg.

Note that continuation onto Stage 2 requires a demonstration of at least 1 or 2 objective responses in subjects with melanoma or TNBC, respectively, in addition to meeting the adverse event requirements detailed above, at either Imprime PGG dose of 4 mg/kg or 2 mg/kg. Please refer to the [Trial Diagram](#) in [Section 2.2](#) for a schema of the study flow from start to end.

In general, any Grade 4 non-infusion or non-hematological AE will lead to the withdrawal of the subject from treatment. A dosing delay of up to 3 weeks is allowed in case of Grade 3 non-hematological AEs to reduce toxicity to baseline or Grade 0-1. Dose levels will be adjusted individually for each study drug.

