**Table 6. Target Imprime PGG Administration Values**

Subject Weight (kg)	Dose Level (mg/kg)	Total Infusion Volume (mL)	Infusion Time (hours)	Rate of Infusion (mL/min)
≤75	4	500	2	4.2
>75 to ≤150	4	750	3	4.2
>150	4	1000	4	4.2
≤75	2	500	2	4.2
>75 to ≤150	2	750	3	4.2
>150	2	1000	4	4.2

**Note:** Concentration and rate calculations are based upon an average weight of 75 kg and are approximate; actual values will differ among subjects based upon total body weight and may therefore be outside of the ranges presented above in [Table 6](#).

Please refer to [Section 5.2.1.2.1](#) for instructions on handling infusion reactions related to the administration of Imprime PGG.

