**4. Label bag appropriately.**

**5. Attach appropriate IV tubing and using an infusion pump infuse at the rate determined by the total infusion volume/infusion time described above.**

- A. Example (For weight <75 kg):
  - Since subject's weight was 70 kg, a 500 mL total fluid volume was calculated. The length of infusion will be 2 hours at a rate of 4.2 mL/min
- B. Example (For weight >75 kg, up to  $\leq$ 150 kg):
  - Since subject's weight was 100 kg, a 750 mL total fluid volume was calculated. The length of infusion will be 3 hours at a rate of 4.2 mL/min

C. Example (For weight >150 kg):

- Since subject's weight was 160 kg, a 1000 mL total fluid volume was calculated. The length of infusion will be 4 hours at a rate of 4.2 mL/min

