All subjects will receive Imprime PGG and pembrolizumab. Imprime PGG will be administered IV at a dose of 4 mg/kg over a 2-hour infusion time period on Day 1, Day 8, and Day 15 of each 3-week cycle for subjects at stage 1. If Stage 1 proceeds without safety concerns necessitating a second cohort at 2 mg/kg, Imprime PGG will be administered to the Stage 2 subjects at a dose of 4 mg/kg IV over a 2-hour infusion time period on Day 1, Day 8, and Day 15 of each 3-week cycle. If enrollment into an additional cohort for 2 mg/kg in Stage 1 is required and dosing proceeds to Stage 2, Imprime PGG will be administered in Stage 2 at a dose of 2 mg/kg IV over a 2-hour infusion time period on Day 1, Day 8, and Day 15 of each 3-week cycle. The pembrolizumab fixed dose of 200 mg will be administered IV over 30 minutes on Day 1 of each 3-week treatment.

Subjects will be dosed until disease progression, death, 2 years of treatment or study completion, whichever occurs first. After treatment discontinuation, subjects will be monitored every 2 months for survival until death or study completion. Study completion is defined as the death of at least 70% of subjects or 3 years after the last subject's first dose, whichever occurs earlier.

Discontinuation of treatment may be considered for subjects who have attained a confirmed CR, who have been treated for at least 24 weeks, and who had at least 2 treatments with study medications beyond the date when the initial CR was declared. Subjects who then experience radiographic disease progression may be eligible for up to 1 year of additional treatment with Imprime PGG + pembrolizumab at the discretion of the Investigator if:

- No cancer treatment was administered since the last dose of pembrolizumab
- The subject meets the safety parameters listed in the Inclusion/Exclusion criteria
- The trial is open

Subjects will resume therapy at the same dose and schedule at the time of initial discontinuation. Response or progression in this resumed course of therapy will not count towards the ORR of the primary endpoint in this trial.

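### Step 2 of the Imprime PGG infusion-reaction instructions gives a time and a rate that agree only for subjects up to 75 kg

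*Protocol*

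**What the plan says.** Protocol 5.2.1.2.1 lists, in preferred order, premedication, a slower infusion and dose reduction.

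- **Step 2, Infusion Time Extension:** the time is to be "lengthened from 2 hours to 4 hours and the infusion flow rate should be adjusted accordingly to 50% of the previous rate". There is one instruction for all subjects.
- **Step 3, Dose Reduction:** for a subject who reacts despite premedication and "despite the infusion time being lengthened, the PI may re-challenge the subject at the next visit by dose reducing" to 2 mg/kg.
- **Repeat of Stage 1 at 2 mg/kg:** toxicity is assessed as before, "with the identical sequential recommendations for any observed infusion reactions".

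The planned infusion depends on weight. Table 6 and Table 14.1 give 500 mL over 2 hours up to 75 kg, 750 mL over 3 hours from above 75 to 150 kg, and 1000 mL over 4 hours above 150 kg. All are at 4.2 mL/min, and the rows are the same for 4 and 2 mg/kg. The worked examples in Appendix 14.1, step 5, repeat this at both doses. For 100 kg: "The length of infusion will be 3 hours at a rate of 4.2 mL/min". For 160 kg: "The length of infusion will be 4 hours at a rate of 4.2 mL/min". Appendix 14.1 also caps the rate at 4.2 mL/min and limits the diluted product to 8 hours at room temperature, administration included.

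Elsewhere the planned time is a flat 2 hours. Protocol 5.2.1.1 says "Imprime PGG will be administered to all subjects at a dose of 4 mg/kg IV over a 2-hour infusion time period", 5.2.2 repeats it, and SAP section 4 says "Imprime PGG will be administered IV at a dose of 4 mg/kg over a 2-hour infusion time period". Sections 5.2.1.1 and 5.2.2 refer on to Appendix 14.1 for details.

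**The concern.** Step 2 is written as if every subject starts from a 2-hour infusion. Where the plan is 3 or 4 hours, its time and its rate describe different infusions, and the protocol does not say which governs. The step is named for the time, the rate is said to follow from the time, and step 3 refers back to the time. A site could therefore reasonably treat 4 hours as the instruction.

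What is at stake is how a reacting subject above 75 kg is managed. A site that follows the time slows the infusion less than the step intends, and may then reduce the Imprime PGG dose after a weaker step 2 than a lighter subject would have had. The same holds in a 2 mg/kg cohort, because both the steps and the planned times carry over.

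**Working it through.** **Inputs.** Volumes, times, rate and the 4.2 mL/min cap are from Table 6 and Appendix 14.1. The 4 hours and the 50% are from step 2. The gap of 15 to 30 minutes and the 30-minute pembrolizumab infusion are from 5.2.1.1.

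**1. Reproduce the planned rate.** Rate = volume / minutes. 500/120 = 750/180 = 1000/240 = 4.167 mL/min, which rounds to the stated 4.2 in every row.

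**2. Apply each half of step 2.** The time reading gives volume / 240 min. The rate reading gives 4.167 / 2 = 2.083 mL/min, and its duration is volume / 2.083.

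| Weight | Plan | Rate over 4 h (mL/min) | Share of planned rate | Time at half rate |
|---|---|---|---|---|
| up to 75 kg | 500 mL, 2 h | 2.083 | 50% | 4 h |
| >75 to 150 kg | 750 mL, 3 h | 3.125 | 75% | 6 h |
| >150 kg | 1000 mL, 4 h | 4.167 | 100% | 8 h |

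Measured against the rounded 4.2 mL/min, the shares are 49.6%, 74.4% and 99.2%. In the middle band the time reading runs 3.125 / 2.083 = 1.5 times as fast as the rate reading. Volume and time do not depend on dose, so the results are the same at 4 and 2 mg/kg.

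**3. Test whether the flat 2-hour time rescues step 2.** If every subject started from 2 hours, 4 hours would be half rate at any weight. At the tabulated volumes this needs 750/120 = 6.25 or 1000/120 = 8.33 mL/min, both above the 4.2 mL/min cap. That reading is not usable above 75 kg.

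**4. Check the storage limit.** Half rate above 150 kg takes 8 hours (1000 / 2.1 / 60 = 7.94 hours at a rounded 2.1 mL/min). That leaves essentially no preparation time within the 8-hour limit.

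**5. Length of Day 1 for a slowed subject in the middle band.**
- Half rate: 6 + 0.25 to 0.5 + 0.5 = 6.75 to 7.0 hours.
- Time reading: 4 + 0.25 to 0.5 + 0.5 = 4.75 to 5.0 hours.

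**The case against.** The best reply is that the rate clause is relative and works at every weight. A site treating a subject on a 3-hour infusion has no 2 hours to lengthen from, but it does have a usable rule: halve the previous rate. On that view the times are only an incomplete example. The steps are also framed as actions the investigator may take and as recommendations, and Table 6 carries the note "Concentration and rate calculations are based upon an average weight of 75 kg and are approximate".

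Much of this stands. The rate clause is workable, which is why the fix can rest on it, and it would overstate the point to say that step 2 cannot be followed above 75 kg. The case above 150 kg also largely removes itself, because leaving a 4-hour infusion at 4 hours is not an extension. What remains is that nothing says the rate governs, and that 4 hours is a plausible misreading in the middle band. The note on approximate values does not help: the planned rate may not exceed 4.2 mL/min, and a slower start makes the planned time longer, so 4 hours would slow it even less.

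The flat 2-hour wording in 5.2.1.1 and 5.2.2 matters less, since both sections point to Appendix 14.1 and routine infusions would probably follow the weight bands. SAP section 4 is a design summary that sends the reader to the protocol for the dosing schedule, so editing it would change no analysis.

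**Conclusion.** The inconsistency is real and minor. It lies in an operational safety instruction and is not a design choice. From above 75 to 150 kg, following the time gives a 25% reduction in rate where 50% is ordered; above 150 kg it gives none. These figures need no assumption beyond the tabulated volumes and times. That the top band is rare is an assumption: with lognormal weights, mean 70 to 80 kg and coefficient of variation 20% to 30%, 0.004% to 1.1% of subjects would exceed 150 kg.

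A reader might infer two stronger claims that the documents do not support.

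- **That about half the subjects are affected, because Table 6 uses an average of 75 kg.** That figure is a basis for concentration and rate calculations, and no enrolment weights are given. Step 2 also matters only for subjects who have an infusion reaction that premedication does not control, and that number is not given either.
- **That the conflict alters the Stage 1 safety decision.** Mitigation under these steps does bear on whether a Grade 3/4 infusion reaction is counted. The rule, however, turns on whether the reaction resolves or falls to Grade 1/2 within Cycle 1 and does not recur in Cycle 2, whichever rate was used. No change in the count is shown, nor any effect on type I error, power, sample size or an SAP analysis.

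**What to change.** Restate step 2 so that the rate governs, for example:

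*Reduce the infusion rate to 50% of the previous rate, which doubles the infusion time (for example 2 h to 4 h up to 75 kg, and 3 h to 6 h for >75 to 150 kg). Above 150 kg, slow as far as the 8-hour room-temperature limit including preparation allows, per pharmacy instruction.*

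The reference should stay with the previous rate and not the Table 6 rate, because actual rates may differ from the table and a subject already below it would otherwise be slowed by less than half. An 8-hour infusion should not be written in for the top band, since it would use up the whole storage limit. The sponsor's pharmacy needs to supply that instruction.

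Optionally, replace the flat 2-hour time in 5.2.1.1 and 5.2.2, for both doses, with a reference to the weight-banded time in Appendix 14.1. SAP section 4 needs no change.

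The cost is one amended sentence, the pharmacy instruction, and longer visits. A slowed subject in the middle band has a Day 1 of about 6.75 to 7.0 hours instead of 4.75 to 5.0 under the time reading, and an Imprime PGG infusion of 6 hours instead of 4 on Days 8 and 15. Step 2 already orders the 50% rate, so up to 150 kg no new requirement is added.

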## **3. Dose Reduction**

If a subject experiences an infusion reaction despite having been administered premedication and despite the infusion time being lengthened, the PI may re-challenge the subject at the next visit by dose reducing the Imprime PGG to 2 mg/kg.

All attempts should be made to ameliorate Grade 3/4 infusion reactions by the Investigator following the 3 recommendations provided above sequentially.

In Stage 1, any Grade 3/4 infusion reactions mitigated by these actions and either resolving or decreasing to Grade 1/2, if this mitigation occurs within Cycle 1 and the Grade 3/4 infusion reaction does not recur in Cycle 2, will not be counted towards the total of > 4 or 33% of Grade 3/4 adverse events which require halting the study in Stage 1 for each individual indication. Only Cycle 1 Grade 3/4 infusion reactions (or those which recur in Cycle 2) will be counted towards the total which would halt advancement to Stage 2.

- In the event there are a total of > 4 or 33% of Grade 3/4 adverse events in Stage 1 which were unable to be ameliorated by the sequential recommendations above, the dose of Imprime PGG will be reduced to 2 mg/kg.
- Stage 1 will be repeated with an additional cohort of n=12 subjects at the reduced dose of 2 mg/kg. Toxicity at the dose of 2 mg/kg will be assessed in this additional Stage 1 cohort in the same manner as was done for the initial dose of 4 mg/kg, with the identical sequential recommendations for any observed infusion reactions.
- Advancement to Stage 2 will be halted if there are > 4 or 33% of Grade 3/4 adverse reactions. Otherwise, subjects will proceed to Stage 2 with all subjects at the new, reduced dose of 2 mg/kg.

Note that continuation onto Stage 2 requires a demonstration of at least 1 or 2 objective responses in subjects with melanoma or TNBC, respectively, in addition to meeting the adverse event requirements detailed above, at either Imprime PGG dose of 4 mg/kg or 2 mg/kg. Please refer to the [Trial Diagram](#) in [Section 2.2](#) for a schema of the study flow from start to end.

In general, any Grade 4 non-infusion or non-hematological AE will lead to the withdrawal of the subject from treatment. A dosing delay of up to 3 weeks is allowed in case of Grade 3 non-hematological AEs to reduce toxicity to baseline or Grade 0-1. Dose levels will be adjusted individually for each study drug.

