## 2.2 Trial Diagram

\* ≤ 4 subjects or 33% of Stage 1 subjects does not include infusion reactions (from either study drug) which were subsequently controlled and reduced in Cycle 1 via ameliorating actions, and which did not recur in Cycle 2

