Grades 3 or 4  Grade 3: Prolonged (ie, not rapidly responsive to symptomatic medication and/or brief interruption of infusion); recurrence of symptoms following initial improvement; hospitalization indicated for other clinical sequelae (eg, renal impairment, pulmonary infiltrates)  Grade 4: Life-threatening; pressor or ventilatory support indicated	
Stop Infusion.            Additional appropriate medical therapy may include but is not limited to:
 
 
Epinephrines**
 
IV fluids
 
Antihistamines
 
NSAIDS
 
Acetaminophen
 
Narcotics
 
Oxygen
 
Pressors
 
Corticosteroids
 
 
Increase monitoring of vital signs as medically indicated until the subject is deemed medically stable in the opinion of the Investigator.            Hospitalization may be indicated.            **In cases of anaphylaxis, epinephrine should be used immediately.  Subject is permanently discontinued from further study drug treatment.
	No subsequent dosing

Appropriate resuscitation equipment should be available at the bedside and a physician readily available during the period of drug administration.

For further information, refer to the Common Terminology Criteria for Adverse Events v4.03 (CTCAE) at <http://ctep.cancer.gov>

In Stage 1, any Grade 3/4 infusion reactions mitigated by these actions and either resolving or decreasing to Grade 1/2, if this mitigation occurs within Cycle 1 and the Grade 3/4 infusion reaction does not recur in Cycle 2, will not be counted towards the total of > 4 or 33% of Grade 3/4 adverse events which require halting the study in Stage 1 for each individual indication. Only Cycle 1 Grade 3/4 infusion reactions not controlled by the above measures (or those which recur in Cycle 2) will be counted towards the total which would halt advancement to Stage 2.

Dose will be managed individually for each study drug.

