### 7.3 Treatment Period (Treatment Cycles)

Study Day 1 is defined as the day of the first dose of study medication.

The study treatment period will be divided into treatment cycles. Each cycle will be 3 weeks in duration and defined by the frequency of pembrolizumab administration. During each cycle, subjects will dose weekly with Imprime PGG for all 3 weeks (Days 1, 8, and 15). Pembrolizumab will be dosed on D1 of each 3-week cycle. Subjects will be dosed until

disease progression or death or study termination or 2 years or until any of the criteria for study drug discontinuation are met (whichever occurs first).

See [Section 5.2.2 Timing of Dose Administration](#) for the order in which the study medications must be administered.

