#### **9.1.6 Interim Analyses**

One interim analysis will be conducted at the end of Stage 1 for each tumor type. For the dose which meets the safety criterion in Stage 1, if at least 1 objective response among 12 evaluable melanoma subjects is not observed, the melanoma cohort will be terminated; if at least 1 objective response among 12 TNBC evaluable subjects are not observed, the TNBC cohort will be terminated. Early stopping at the interim analysis will only occur for futility, not efficacy. Adverse events including  $\geq$  Grade 3 events will be summarized at the time of the interim analysis.

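### SAP 4 reverses the Stage 1 infusion-reaction exemption and misprints its limit; secondarily, the 4 mg/kg safety count can omit a subject cut to 2 mg/kg, and no described display gives the count both ways

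*Protocol*

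**What the plan says.** **Limit.** Protocol 2.1 and 9.1.1 let a dose proceed if at most 4 of 12 Stage 1 subjects in a tumor type have Grade 3/4 events in Cycle 1. With more than 4, Imprime PGG falls to 2 mg/kg and Stage 1 is repeated. SAP 4 gives the same pass and fail limits.

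**Exemption in the Protocol.** Section 5.2.1.2.1 lists three sequential actions: premedication, a longer infusion, and a dose cut. On the last, "the PI may re-challenge the subject at the next visit by dose reducing the Imprime PGG to 2 mg/kg". It then exempts from the count "In Stage 1, any Grade 3/4 infusion reactions mitigated by these actions and either resolving or decreasing to Grade 1/2", provided this happens within Cycle 1 and the reaction does not return in Cycle 2. The footnote in 2.2 exempts reactions "which were subsequently controlled and reduced in Cycle 1 via ameliorating actions, and which did not recur in Cycle 2". Section 5.2.1.2.2 agrees: "Only Cycle 1 Grade 3/4 infusion reactions not controlled by the above measures (or those which recur in Cycle 2) will be counted".

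**Exemption in the SAP.** The parenthesis in SAP 4 exempts Cycle 1 Grade 3/4 infusion reactions that resolve or drop to Grade 1/2 and do recur in Cycle 2. It describes the total as 4 or more.

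**Reporting.** Under Protocol 9.1.6, events of Grade 3 or higher are covered: "Grade 3 events will be summarized at the time of the interim analysis". SAP 5.1 reports that an informal Stage 1 look has taken place. SAP 12.1, 12.2 and 12.4 describe summaries or listings of Grade III/IV events, infusion reactions by maximum grade, and dose reductions. None of these applies the exemption.

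**The concern.** The safety count is one of the two conditions for taking 4 mg/kg into Stage 2; the other is the response requirement. Read literally, SAP 4 drops the subjects the Protocol most wants counted, those whose severe reaction came back, and counts those whose reaction was controlled for good. Its total of 4 or more also invites failing a dose at exactly 4 of 12, which the Protocol passes. Since the Stage 1 look is complete, a report stating only that 4 mg/kg met the criterion would not show which rule stood behind it.

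The second issue lies in the Protocol's own rule. A subject who reacts at 4 mg/kg, is cut to 2 mg/kg within Cycle 1 and then has no recurrence meets the exemption. The Cycle 2 check may itself have been made at 2 mg/kg. Such a subject is direct evidence on the choice between 4 and 2 mg/kg, yet is absent from the 4 mg/kg count.

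**Working it through.** **1. The two rules side by side**, for a subject with a Cycle 1 Grade 3/4 infusion reaction:

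| Course | Protocol 2.2, 5.2.1.2.1, 5.2.1.2.2 | SAP 4, read literally |
|---|---|---|
| Not controlled in Cycle 1 | counted | counted |
| Controlled, no recurrence in Cycle 2 | not counted | counted |
| Controlled, recurs in Cycle 2 | counted | not counted |

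The last two rows are reversed. The documents give no rates for these courses, so the net effect of the reversal cannot be sized.

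**2. The plan's own figures.** No operating characteristics are given for the safety rule. Those for response in Protocol 9.1.1 reproduce. Early termination under the null is 0.95^12 = 0.540 for both tumor types. Exact two-stage type I error is 0.0500 (melanoma) and 0.0452 (TNBC); power is 0.902 and 0.906. The safety count does not enter these calculations.

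**3. Effect of the misprinted limit.** Let X be the number of counted subjects among 12 and b the assumed chance that a subject is counted. Moving the failing limit from more than 4 to 4 or more lowers the chance of passing by P(X = 4) = 495 × b^4 × (1 − b)^8. At b = 0.15 this is 495 × 0.00050625 × 0.27249 = 0.068, so passing falls from 0.9761 to 0.9078.

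**4. Is the dose-cut path possible?** Protocol 7.3 gives Imprime PGG on Days 1, 8 and 15 of each cycle, and an antihistamine is already given on Cycle 1/Day 1. A reaction on Day 1, a longer infusion and second reaction on Day 8, and a cut on Day 15 all fit within Cycle 1. No text excludes control by dose cut from the exemption. The path is narrow: the cut is optional, and for a Grade 3/4 reaction handled as a pembrolizumab reaction Table 2 says "Subject is permanently discontinued from further study drug treatment".

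**5. Size of the dose-cut issue.** Simplest case: 4 counted plus 1 exempt reads as 4/12 = 33.3%, a pass; with the exempt subject it is 5/12 = 41.7%, above the limit. More generally, let r be the chance that a subject takes the dose-cut path, independent of b. The fuller count uses p = 1 − (1 − b)(1 − r). Both b and r are assumptions.

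| b | P(X ≤ 4) as written | r = 2%: fuller count (difference) | r = 5%: fuller count (difference) |
|---|---|---|---|
| 10% | 0.9957 | 0.9912 (0.0045) | 0.9791 (0.0165) |
| 15% | 0.9761 | 0.9634 (0.0127) | 0.9370 (0.0391) |
| 25% | 0.8424 | 0.8099 (0.0325) | 0.7559 (0.0864) |

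The difference is the chance that the count as written passes while the fuller count exceeds 4. The chance of at least one such subject is 1 − (1 − r)^12 = 0.215 or 0.460 in one cohort, and 1 − (1 − r)^24 = 0.384 or 0.708 over both tumor types.

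**6. Would a reader see both counts?** SAP 12.2 splits events by time at 3, 6 and 12 months. With the SAP's month of 30.4375 days, the first band is 3 × 30.4375 = 91.3 days, or 91.3/21 = 4.3 cycles. No described summary isolates Stage 1, Cycle 1, or sets the count with and without dose-cut subjects against 4 of 12.

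**The case against.** The exemption is deliberate and pre-specified, and individual dose reduction is part of the regimen. On that view the count judges a 4 mg/kg starting dose with stepwise mitigation, not strict tolerance of 4 mg/kg. This is a fair reading, and it is why the dose-cut issue calls for disclosure and not a new rule.

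SAP 4 is a design recap, SAP 1 sends readers to the Protocol, and the stray total sits between correct limits. A slip is the likeliest explanation. It is still a decision rule printed wrongly in the current SAP.

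A reader might infer that dose-cut subjects vanish from the safety reporting. The documents do not support that: the Grade 3 or higher interim summary and the tables and listings in SAP 12.1, 12.2 and 12.4 would include them and allow a recount. Only the two-way count is missing. The display lists that SAP 10 and 11 place in Sections 15.1 and 15.2 are not in the text available, so this absence concerns described displays only.

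A reader might also infer that the Protocol contradicts itself, because one sentence in 5.2.1.2.1, "Only Cycle 1 Grade 3/4 infusion reactions (or those which recur in Cycle 2) will be counted towards the total", omits the condition that the reaction was not controlled. The sentence before it and the bullet after it, which counts events the sequential steps could not ameliorate, settle the meaning, as do 2.2 and 5.2.1.2.2.

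Finally, the 2% and 5% path rates have no source in the documents. That is correct; they show a range and estimate nothing.

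**Conclusion.** SAP 4 misstates the Stage 1 safety rule in two respects, the direction of the recurrence condition and the limit, and should be corrected. The documents do not say which rule was applied at the completed look, and they give no ground for concluding that the Stage 2 decision was wrong.

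The dose-cut gap is real on the text but minor. Under independent events with assumed rates (background 10% to 25%, path 2% to 5%), the fuller count changes the verdict with probability between 0.5 and 8.6 percentage points. The two counts may well differ while the verdict seldom does. The response hypotheses, thresholds and error rates are unaffected.

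**What to change.** 1. In SAP 4, exempt only reactions that were mitigated in Cycle 1 and do not recur in Cycle 2, and give the failing limit as more than 4.
2. State in the study report which rule was applied at the Stage 1 look.
3. For each tumor type, add one descriptive row: Stage 1 subjects at 4 mg/kg with Cycle 1 Grade 3/4 events, with and without those exempted through a cut to 2 mg/kg. The limit of 4 was set for the count as the Protocol defines it, so the fuller count is not tested against that limit and does not reopen the Stage 2 decision.

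The cost is a SAP wording correction, a sentence in the report, and one table row per tumor type from infusion, infusion-reaction and dose-modification data already collected. The downside for the sponsor is a possibly less favourable safety statement for 4 mg/kg. Patient management, enrollment and the response test do not change, and no protocol amendment is needed.
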